7.6.3 Quality of Life and Patient Reported Outcome Assessment

Quality of life (QOL) questionnaires will be assessed using EQ-5D-5L and pain assessment rating scale at the time point as indicated in the Schedules of Assessments [Table 1] and [Table 2]. The PRO data will be completed on paper forms by the subject and should always be completed first at every schedule clinic visit prior to dosing and any other study assessments, especially discussion of disease status. Subjects who do not speak a language for which translated QOL questionnaires are available or who is illiterate and therefore will not be able to complete the QOL questionnaires may be enrolled into the study and exempted from completing QOL questionnaires after consultation with the sponsor.

7.6.3.1 Cohorts 1 to 8:

7.6.3.1.1 Global Pain Assessment

The subject will rate his/her pain on a 0 to 10 scale that best describes the pain at its worst in the last 24 hours. See [Appendix 12.11 Pain Assessment].

7.6.3.1.2 Euro Quality of Life-5 Dimensions

The EQ-5D-5L is a standardized instrument developed by the EuroQOL Group for use as a generic, preference-based measure of health outcomes. It is applicable to a wide range of health conditions and treatments and provides a simple descriptive profile and a single index value for health status. The EQ-5D-5L is a 5-item self-reported measure of functioning and well-being, which assesses 5 dimensions of health, including mobility, selfcare, usual activities, pain/discomfort, and anxiety/depression. Each dimension comprises 5 levels (no problems, slight problems, moderate problems, severe problems, extreme problems). A unique EQ-5D-5L health state is defined by combining 1 level from each of the 5 dimensions. This questionnaire also records the respondent's self-rated health status on a

vertical graduated (0 to 100) visual analogue scale [Herdman et al, 2011]. See [Appendix 12.12 EQ-5D-5L].

7.6.3.2 Cohort 9

7.6.3.2.1 EORTC QLQ H&N43

The EORTC H&N43 contains 43 items of 6 multi-item and 13 single-item symptom subscales namely pain, swallowing, senses problems, speech problems, trouble with social eating, less sexuality, teeth, dry mouth/sticky saliva, body image, shoulder pain, skin problems, anxiety, trouble with social contact, opening mouth, coughing, lymphedema, problems wound healing, weight loss, neurological problems.

7.6.3.2.2 Global Pain Assessment

The subject will rate his/her pain on a 0 to 10 scale that best describes the pain at its worst in the last 24 hours. See [Appendix 12.11 Pain Assessment].

7.6.3.2.3 PRO-CTCAE

Three questions will be utilized from the PRO-CTCAE to obtain subject assessment of fatigue and diarrhea symptoms.

7.6.3.3 FACT-G

Functional Assessment of Cancer Therapy – General (FACT-G) Version 4 is a 27-item questionnaire designed to measure four domains of HRQOL in cancer patients: Physical, social, emotional, and functional well-being. Original development and validation involved 854 patients with cancer and 15 oncology specialists. Subjects with cancer aged 18 years and older are asked to recall the past 7 days and complete the questionnaire. EV-202 cohort 9 will include a single question from the “Physical Well-Being” domain, GP5 “I am bothered by side effects of treatment” which is self-scored from “0 to 4” (0 - not at all; 1 - A little bit; 2 - Somewhat; 3 - Quite a bit; 4 - very much).

7.7 Total Amount of Blood

The total amount of blood for each subject will vary depending on the course of their disease, duration on treatment and local laboratory requirements. At any time during the study, if any laboratory abnormalities are found for a subject, additional blood may be drawn for safety monitoring.

For cohorts 1 to 8, the maximum amount of blood collected is approximately 52 mL on cycle 1 day 1, 41 mL on cycle 1 day 8, and 48 mL on cycle 1 day 15. The maximum amount of blood collected for subjects that participate from cycle 2 up to cycle 6 and completes the EOT visit is approximately 185 mL.

For cohort 9, the maximum amount of blood collected is approximately 52 mL on cycle 1 day 1, 41 mL on cycle 1 day 8, and 8 mL on cycle 1 day 15. The maximum amount of blood collected for subjects that participate from cycle 2 up to cycle 6 and completes the EOT visit is approximately 233 mL.

8 DISCONTINUATION

8.1 Discontinuation of Individual Subject(s) From Study Treatment

A discontinuation from treatment is defined as a subject who enrolled in the study and for whom study treatment is permanently discontinued for any reason.

The subject is free to withdraw from the study treatment and/or study for any reason and at any time without giving reason for doing so and without penalty or prejudice. The investigator is also free to discontinue the subject from study treatment or to terminate a subject's involvement in the study at any time if the subject's clinical condition warrants it.

The reason for discontinuation from study treatment must be documented in the subject's medical records.

A subject must discontinue study treatment for any of the following reasons:

- Subject develops documented radiological disease progression (iCPD per iRECIST) in cohort 9).
- Subject starts a new anticancer therapy.
- Subject develops unacceptable toxicity.
- Female subject becomes pregnant.
- Investigator decides it is in the subject's best interest to discontinue.
- Subject requests to stop treatment.
- Subject is noncompliant with the protocol based on the investigator or medical monitor assessment.
- Subject has continuous dose interruption > 6 months.
- Study is terminated by sponsor.

For subjects in cohort 9, Pembrolizumab may be administered for up to a total of 35 cycles (approximately 2 years). Subjects who experience an unacceptable AE that is clearly attributable only to pembrolizumab may continue on enfortumab vedotin monotherapy until a discontinuation criterion is met. Subjects who experience unacceptable toxicity that is clearly attributable only to enfortumab vedotin may continue on pembrolizumab monotherapy up to a maximum of 35 cycles.

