- Subject develops documented radiological disease progression (iCPD per iRECIST in cohort 9)
- Subject starts on a new anticancer therapy
- Subject develops unacceptable toxicity
- Female subject becomes pregnant
- Investigator decides it is in the subject's best interest to discontinue
- Subject requests to stop treatment
- Subject is noncompliant with the protocol based on the investigator or medical monitor assessment
- Subject has continuous dose interruption > 6 months
- Study is terminated by sponsor

All subjects who discontinue study treatment will remain in the study and must continue to be followed for protocol-specific follow-up procedures. Subjects may be discontinued from the study for any of the following reasons:

- Lost to follow-up
- Death
- Subject withdrawal of consent
- Study termination by sponsor

On a periodic basis, a Safety Monitoring Committee (SMC) will review the safety data of the study. The SMC may recommend whether the study should be terminated, modified or continue unchanged based on ongoing reviews of study safety data.

Investigational Product(s):

Name:

Enfortumab vedotin

Dose, Mode of Administration and Dose Modification:

Enfortumab vedotin at a dose of 1.25 mg/kg will be administered as an IV infusion on days 1, 8 and 15 of every 28-day cycle for cohorts 1 to 8 and on days 1 and 8 of every 21-day cycle for cohort 9. Enfortumab vedotin will be administered based on the subject's actual body weight on day 1 of each cycle except for subjects weighing greater than 100 kg; in such cases, the dose will be calculated based on a maximum weight of 100 kg. Enfortumab vedotin will be administered intravenously over an approximately 30-minute period.

Dose reduction to 1, 0.75 or 0.5 mg/kg will be allowed depending on the type and severity of toxicity. Subjects requiring a dose reduction may be re-escalated by 1 dose level (i.e., subjects reduced to 0.75 mg/kg may only be re-escalated to 1 mg/kg) provided the toxicity does not require study drug discontinuation and has returned to baseline or \leq grade 1. If the toxicity recurs, re-escalation will not be permitted. Subjects with \geq grade 2 corneal AEs will not be permitted to dose re-escalate.

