8.2 Discontinuation of Individual Subject(s) From Study

All subjects who discontinue study treatment will remain in the study and must continue to be followed for protocol-specific follow-up procedures as outlined in the Schedules of Assessments [Table 1] and [Table 2]. The only exception to this is when the subject specifically withdraws consent for any further contact with him/her or persons previously authorized by the subject to provide this information. A subject may be discontinued from the study for any of the following reasons:

- Lost to follow-up
- Death
- Subject withdrawal of consent
- Study termination by sponsor

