10.3 Major Protocol Deviations

A protocol deviation is generally an unplanned excursion from the protocol that is not implemented or intended as a systematic change. All deviations from the protocol are to be recorded. A protocol waiver is a documented prospective approval of a request from an investigator to deviate from the protocol. Protocol waivers are strictly prohibited.

The investigator is responsible for ensuring the study is conducted in accordance with the procedures and evaluations described in this protocol and must protect the rights, safety and well-being of subjects. The investigator should not implement any deviation from, or changes of, the protocol, unless it is necessary to eliminate an immediate hazard to subjects.

A major protocol deviation is one that may potentially impact the completeness, accuracy or reliability of data contributing to the primary endpoint or affect the rights, safety or well-being of a subject. Major protocol deviations will have additional reporting requirements.

When a major deviation from the protocol is identified for an individual subject, the investigator or designee must ensure the sponsor is notified. The sponsor will follow-up with the investigator, as applicable, to assess the deviation and the possible impact to the safety and/or efficacy of the subject to determine subject continuation in the study.

The major protocol deviation criteria that will be summarized at the end of the study are as follows:

PD1 - Entered into the study even though the subject did not satisfy entry criteria

PD2 - Developed withdrawal criteria during the study and was not withdrawn

PD3 - Received wrong treatment or incorrect dose. For enfortumab vedotin, incorrect dose will be defined as less than or greater than 10% from the intended dose. For pembrolizumab, any dose of 1000 mg or greater will be considered incorrect dose.

PD4 - Received excluded concomitant treatment

The investigator will also assure that deviations meeting IRB/IEC and appropriate regulatory authorities' criteria are documented and communicated appropriately. All documentation and communications to the IRB/IEC and appropriate regulatory authorities will be provided to the sponsor and maintained within the Trial Master File.

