5.2.3 Progression-free Survival per Investigator Assessment

PFS is defined as the time from the date of first dose of study drug to the date of first documented radiological disease progression (PD) per RECIST Version 1.1 by investigator assessment or death due to any cause, whichever comes first. PFS will be censored as the following:

- If a subject has neither PD nor death, PFS will be censored at the date of last evaluable radiological tumor assessment.
- If a subject starts a new anti-cancer treatment before any PD event or death, PFS will be censored at the date of last evaluable radiological tumor assessment prior to the date of new anti-cancer treatment.
- If a subject has PD or death immediately after two or more consecutive missed radiological tumor assessments, DOR will be censored at the last evaluable radiological tumor assessment prior to two or more missed radiological tumor assessments.
- If a subject does not have evaluable postbaseline radiological assessment, PFS will be censored at the first dose date of study drug.

For a subject who is censored, the last evaluable radiological tumor assessment refers to the subject's last radiological tumor assessment where the response is CR, PR or SD.

New anti-cancer treatment includes therapies captured on new anti-cancer therapy eCRF and new radiation/palliative radiation therapies captured on new radiation therapy eCRF that will impact target and/or non-target lesions.

PFS (in months) will be calculated as:

$$[(\text{Date of documented disease progression or death or censoring}) - (\text{Date of first dose of study drug}) + 1] / 30.4375$$

When a cutoff date is applied to PFS analysis, tumor assessment, death and new anti-cancer treatment occurring after the cutoff date will be excluded from the analysis.

The primary analysis population for PFS is FAS.

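### Protocol 8.1 lets the investigator take a subject out of the study on clinical condition, an exit that 8.2 does not allow; any such removal is censored by default and may flatter PFS, DOR and OS.

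*Protocol*

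**What the plan says.** Protocol 8.1, the section on stopping study treatment, gives the investigator two powers joined by an alternative: to take the subject off treatment, or "to terminate a subject's involvement in the study at any time if the subject's clinical condition warrants it".

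The synopsis says the opposite about follow-up: "All subjects who discontinue study treatment will remain in the study and must continue to be followed for protocol-specific follow-up procedures". Section 8.2 repeats that rule and adds: "The only exception to this is when the subject specifically withdraws consent for any further contact with him/her" (or with people the subject had authorized to give information). It then introduces the exits with "A subject may be discontinued from the study for any of the following reasons" and lists four: loss to follow-up, death, withdrawal of consent and termination by the sponsor. The synopsis has the same four.

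Protocol 10.3 has the sponsor assess a major deviation with the investigator "to determine subject continuation in the study". Deviation is not on the 8.2 list either.

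The SAP has no rule for a subject removed by the investigator. For PFS, section 5.2.3 states: "If a subject has neither PD nor death, PFS will be censored at the date of last evaluable radiological tumor assessment". Section 5.2.1 does the same for DOR. Section 5.2.4 censors OS at the last known alive date or the analysis cutoff, whichever is earlier.

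**The concern.** A site that uses the second power in 8.1 breaches 8.2, and the two sections cannot both be followed. The statistical interest lies in the trigger. Kaplan-Meier assumes that a censored subject has the same outlook as those still at risk. A subject removed because of clinical condition may well have a worse one. If later progression or death then goes unrecorded, the PFS, DOR and OS curves sit too high. The cohorts are single-arm with about 40 subjects, so no control arm shares the error, and two removals are already 2/40 = 5% of a cohort.

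The planned outputs would not show the cause. SAP 6.4.2.1 and 6.4.2.3 name two censoring types, no event and new anti-cancer treatment, and these removals would fall under the first. Section 8.1 requires a documented reason for stopping treatment but not for ending study involvement.

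**Working it through.** The plan gives no figure on this point, so there is none to reproduce. The check is a comparison of the passages, followed by an illustration of size.

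**Passages side by side**

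| Place | Who may leave follow-up |
|---|---|
| Protocol 8.1 | Any subject, if the investigator judges that clinical condition warrants it |
| Protocol 8.2 and synopsis | Four listed reasons; no investigator decision |
| Protocol 7.1.5 (survival contacts) | Stops at death, consent withdrawal, loss to follow-up or study closure (the sponsor may also end collection for a whole cohort) |
| Protocol 10.3 | Continuation decided after a major deviation |
| SAP 5.2.1, 5.2.3, 5.2.4 | No rule for such removals; default censoring applies |

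The conflict between 8.1 and 8.2 is in the current text. If a subject is removed before any evaluable postbaseline scan, and no death is known, SAP 5.2.3 censors PFS at the first dose date.

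**Illustration of size**

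Assumptions, none of them from the documents: exponential event times with true median m; a random fraction f of subjects censored L months before their event; the event never learned of; no other censoring.

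With hazard h = ln 2 / m, at time t:

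- proportion at risk: (1 − f)e^(−ht) + f·e^(−h(t+L))
- event density: (1 − f)·h·e^(−ht)

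Their ratio does not depend on t, so the Kaplan-Meier curve stays exponential, with apparent median

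m* = m × [1 + f/(1 − f) × 2^(−L/m)].

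OS, m = 8 months, L = 1 month, 2^(−1/8) = 0.917:

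- f = 5%: 8 × (1 + 0.0526 × 0.917) = 8.4 months
- f = 10%: 8 × (1 + 0.1111 × 0.917) = 8.8 months
- 12-month OS: true value 2^(−12/8) = 35.4%; at f = 5%, 2^(−12/8.39) = 37.1%; at f = 10%, 2^(−12/8.82) = 38.9%

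PFS, m = 4 months, L = 1 month, 2^(−1/4) = 0.841:

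- f = 5%: 4 × (1 + 0.0526 × 0.841) = 4.2 months
- f = 10%: 4 × (1 + 0.1111 × 0.841) = 4.4 months

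Simulated exponential times give the same values. At f = 0 the assumed medians return.

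For scale, if all 40 deaths were observed under this model, the 95% interval around a median of 8 months would be 8 × exp(±1.96/√40), about 5.9 to 10.9 months. A shift of 0.4 to 0.8 months lies well inside it.

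**The case against.** The strongest reply is that 8.2 is the section that governs leaving the study, and it is explicit. The 8.1 phrase is one general sentence in a section about treatment, and its list of mandatory reasons covers treatment only. Long-term follow-up is a 12-weekly contact for which a telephone call suffices (Protocol 4.1), so poor condition gives little reason to end it. A site may never use the clause. This stands as a limit on size. It does not remove the contradiction.

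Several stronger readings are tempting, and the documents do not support them:

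- **That nothing in the plan would reveal these exits.** Protocol 9.3.2 and SAP 6.2.1 tabulate discontinuation of post-treatment and long-term follow-up with the primary status. What is missing is a category for this reason in 8.2 and a separate censoring type in the SAP.
- **That 10.3 adds to the bias.** Its trigger is a protocol deviation (eligibility, failure to withdraw, wrong dose, excluded medication), which is not tied to prognosis. It conflicts with the 8.2 list, but no direction of bias follows.
- **That every removed subject's death is lost.** Protocol 7.3.5 requires all deaths up to 30 days after the last dose to be reported as SAEs even when due to progression, extended to 90 days after pembrolizumab in cohort 9. Section 7.3.3 continues adverse event follow-up after a subject leaves the study. Many deaths soon after removal from treatment would still count. Later deaths and unscanned progressions would not.
- **That 8.1 speaks of deterioration.** It says clinical condition. A link to poor prognosis is plausible but is an inference.

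**Conclusion.** The contradiction between 8.1 and 8.2 is real and should be removed. If the 8.1 exit is used, default censoring may be informative, and the likely direction is upward for PFS, DOR and OS.

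The size cannot be known from the documents, which give no expected number of removals. The illustrative rise in median OS from 8 to about 8.4 to 8.8 months rests on assumed exponential survival, 5% to 10% of subjects removed, a one-month lead and no recovery of deaths. The SAE reporting rule makes it an upper illustration for those fractions.

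A reader might infer that the trial's main result is at risk. It is not. The response evaluable set keeps subjects who are no longer in response follow-up (SAP 4.2), insufficient data count as non-response (SAP 6.9.2), and the numerical go/no-go boundaries use confirmed responders (SAP 6.7). PFS, DOR and OS are secondary and descriptive. The point is minor.

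**What to change.** **Protocol 8.1.** Strike the alternative that lets the investigator end study involvement, so that the sentence covers study treatment only. Add that scan and survival follow-up continue under 8.2 unless consent for further contact is withdrawn. The investigator's discretion over study treatment is unchanged.

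**Protocol 10.3.** Reconcile the phrase on continuation in the study with the exit list in 8.2. How that is resolved is for the sponsor.

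**SAP.** An amendment cannot reach removals that have already happened: the cohort 5 primary analysis was completed in July 2022, and the planned study period ends about 1Q2026. Report the number of investigator removals by cohort, separately from other no-event censoring. Add a sensitivity analysis of PFS, DOR and OS that counts each removal as an event, for example at the date of removal. Read with the default analysis, it shows how far the estimates depend on these subjects.

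**Cost.** Small wording changes in one amendment, one extra disposition line and one sensitivity analysis. No visits are added beyond those 8.2 already requires.

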8.2 Discontinuation of Individual Subject(s) From Study

All subjects who discontinue study treatment will remain in the study and must continue to be followed for protocol-specific follow-up procedures as outlined in the Schedules of Assessments [Table 1] and [Table 2]. The only exception to this is when the subject specifically withdraws consent for any further contact with him/her or persons previously authorized by the subject to provide this information. A subject may be discontinued from the study for any of the following reasons:

- Lost to follow-up
- Death
- Subject withdrawal of consent
- Study termination by sponsor

8.2.1 Lost to Follow-up

Every reasonable effort is to be made to contact any subject lost to follow-up during the course of the study to complete study-related assessments and record outstanding data.

8.3 Discontinuation of the Study Site

If an investigator intends to discontinue participation in the study, the investigator must immediately inform the sponsor and, if applicable, the head of the study site.

8.4 Discontinuation of the Study

The sponsor may terminate this study prematurely, either in its entirety or at any study site, for reasonable cause provided that written notice is submitted in advance of the intended termination. Advance notice is not required if the study is stopped due to safety concerns. If the sponsor terminates the study for safety reasons, the sponsor will immediately notify the investigator and subsequently provide written instructions for study termination.

9 STATISTICAL METHODOLOGY

A statistical analysis plan (SAP) will be written to provide details of the analysis, along with specifications for tables, listings and figures to be produced. The SAP will be finalized before the database hard-lock at the latest. Changes from the planned analyses in the final SAP that impact the statistical analyses will be justified in the clinical study report (CSR).

In general, data will be summarized by cohort and overall with descriptive statistics for continuous endpoints, and frequency and percentage for categorical endpoints. Kaplan-Meier estimates will be provided for time-to-event endpoints.

9.1 Sample Size

The planned sample size for cohorts 1 to 8 is 40 subjects in each cohort. Assuming the reference ORR for the 7 tumor types chosen for the study, ranges from 10% to 20%, and at least a 10% absolute increase in ORR is considered clinical meaningful improvement, the sample size of 40 subjects allows an 80% confidence interval of enfortumab vedotin ORR to exclude the reference ORR. The actual sample size for each cohort may be less than the planned sample size depending on the ORR analysis result at the planned interim analysis. Per Bayesian optimal design for phase 2 (BOP2), the enrollment of a cohort maybe stopped after interim analysis.

The planned sample size for cohort 9 is 40 subjects. Assuming the reference ORR for cohort 9 is 20%, and at least a 25% absolute increase in ORR is considered clinical meaningful improvement for combination therapy, the sample size of 40 subjects allows a 92% power to detect a statistically significant difference at type 1 error rate of 1-sided 0.025. The actual sample size for cohort 9 may be less than the planned sample size depending on the ORR analysis result at the planned interim analysis. Per Bayesian optimal design for phase 2 (BOP2), the enrollment of a cohort maybe stopped after interim analysis.

